### 3. OBJECTIVE(S) AND ENDPOINT(S)

Objectives	Endpoints
Primary	

 
To determine the efficacy of tafenoquine co-administered with DHA-PQP for the radical cure of P. vivax malaria, relative to DHA-PQP alone at 6 months.
 
	
 
Subjects with relapse-free efficacy six months post-dosing (i.e. clearance of initial infection without subsequent microscopically confirmed recurrence during the 6 month follow up).
 

Secondary	

 
To characterize the efficacy of tafenoquine relative to primaquine when co-administered with DHA-PQP.
 
	
 
Subjects with relapse-free efficacy six months post-dosing.
 

 
To determine the efficacy of primaquine co-administered with DHA-PQP relative to DHA-PQP alone.
 
	
 
Subjects with relapse-free efficacy six months post-dosing.
 

 
To determine the efficacy of tafenoquine co-administered with DHA-PQP relative to a DHA-PQP alone at four months.
 
	
 
Subjects with relapse-free efficacy four months post-dosing.
 

 
To determine the blood stage efficacy of tafenoquine in subjects with P. vivax malaria when co-administered with DHA-PQP.
 
	
 
Time to relapse.
 
Time to fever clearance (in subjects with fever at baseline).
 
Time to parasite clearance.
 
Percentage of subjects with recrudescence (blood stage treatment failure) on or before Day 14 (i.e. a recurrence of P. vivax parasites which is genetically homologous to the baseline P. vivax infection).
 

 
To assess the safety of tafenoquine in subjects with P. vivax malaria when co-administered with DHA-PQP.
 
	
 
Incidence and severity of adverse events and SAEs.
 
Incidence of clinically significant abnormal clinical laboratory tests, ECGs and vital signs.
 
Key safety endpoints of interest:
 

Objectives	Endpoints

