## 9.4 Key Elements of Analysis Plan

The primary comparison of interest will be the treatment difference over 6 months between DHA-PQP plus TQ and DHA-PQP alone using a Logrank test. Point estimates will be derived from Kaplan Meier methods and include all subjects in the ITT population. Subjects who were lost to follow up or did not relapse by the end of the follow up will be censored at the time of withdrawal or completion of the study.

Note that data from the Day 195 visit will be not used in the assessment of relapse at 6 months. The last data to be used is the data from the Day 180 visit.

Subjects will be considered to have demonstrated relapse-free efficacy at six months if **all** of the following are true:

- Subject had a non-zero *P. vivax* asexual parasite assessment on Day 1. (Subjects who do not meet this criteria will be censored, with time to relapse censored at 0 days).
- Subject demonstrated initial clearance of *P. vivax* parasitemia. (Subjects who do not meet this criteria will be considered to have relapsed with time to relapse = 0 days).
- Subject had a non-zero *P. vivax* asexual parasite assessment on Day 1. (Subjects who do not meet this criteria will be censored, with time to relapse censored at 0 days)
- Subject demonstrated initial clearance of *P. vivax* parasitaemia. (Subjects who do not meet this criteria will be considered to have relapsed with time to relapse = 0 days)
- Subject has no positive asexual *P. vivax* parasite count at any assessment prior to the scheduled Day 180 visit following initial parasite clearance. (Subjects who do have a positive count will be considered to have relapsed with time to relapse = (date of first positive count) – (date of Day 1 visit) days).
- Subject did not take a concomitant medication with anti-malarial activity (excluding study treatment) at any point between day 1 and the scheduled Day 180 visit. (Subjects who did take a drug with anti-malarial activity but never had a positive asexual *P. vivax* parasite count after initial clearance will be censored, with time to relapse censored at (date of medication start) – (date of Day 1 visit) days).
- Subject has a scheduled Day 180 assessment, and is parasite free at this time point. (Subjects who do not have a Day 180 visit and have not already failed or been censored will be censored at (date of final parasite assessment) – (date of Day 1 visit) days).

All statistical testing will be performed using a significance level of 0.05.

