2. SUMMARY OF KEY PROTOCOL INFORMATION

2.1. Changes to the Protocol Defined Statistical Analysis Plan

Gastrointestinal (GI) tolerability was listed as an endpoint in the protocol. Data from phase 3 studies of tafenoquine, reported since the protocol was finalised, have abated previous concerns with regards GI tolerability, and hence this endpoint will not be specifically analysed. GI AEs will however still be reported in summaries of adverse events (AEs).

Additional study populations have been defined:

The Safety Open Label, Primaquine phase, Non-Relapsers (Safety OL) Population, has been defined for the summaries of adverse events for the participants who did not relapse during the double-blind phase and went onto the open-label primaquine phase at the end of the study.

The PK population has been defined as all participants for whom at least one systemic tafenoquine concentration, and associated sample date/time is available.

The ITT population has been renamed to the microbiologic-intent-to-treat population (mITT) and the definition updated to include the need for participants to have microscopically-confirmed *P. vivax* parasitemia at baseline.

The primary analysis uses a Cox's proportional hazards model as opposed to the log rank test as described in the protocol.

At the time of finalising the full RAP, it had been established that a blinded data review was not required due to 150 participants having been randomised. Details of the blinded data review are therefore not included in the RAP. It was also known that recruitment was from 2 battalions.

For the analysis of dichotomous endpoints, logistic regression analysis will be performed as opposed to exact methods as defined in the protocol. This enables battalion to be adjusted for in analyses.

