11.6.3. Efficacy**Efficacy endpoints****Relapse free efficacy at six months**

Relapse is defined as any recurrence of *P. vivax* malaria after clearance of the initial infection.

Participants will be considered to have demonstrated relapse-free efficacy at six months if all of the following are true (also described in [Figure 1](#)):

Participant had a non-zero *P. vivax* asexual parasite count at baseline. Participants who do not meet this criterion will be censored, with time to relapse censored at 0 days.

Participant demonstrated initial clearance of *P. vivax* parasitemia. This is defined as two negative asexual *P. vivax* parasite counts, with at least 6 hours between the counts, and no positive counts in the interval. Participants who do not meet this criterion will be censored with time to relapse censored at 0 days.

Participant has no positive asexual *P. vivax* parasite count at any assessment prior to or on Day 180 visit following initial parasite clearance. Participants who do have a positive count will be considered to have relapsed with time to relapse = (date of first positive count) – (date of Study Day 1) days.

Participants did not take a concomitant medication with anti-malarial activity (excluding study treatment) at any point between Study Day 1 and their last parasite assessment. Participants who did take a drug with anti-malarial activity but never had a positive asexual *P. vivax* parasite count after initial clearance will be censored with time to relapse censored at (date of last negative parasite assessment prior to concomitant medication start) – (date of Study Day 1) days. If a participant has not had a negative assessment prior to the concomitant medication start date, they will be censored at 0 days.

[figure not shown]
Efficacy endpoints

Participant is parasite-free at 6 months. This is defined as a negative asexual *P. vivax* parasite count at the first parasite assessment performed on or after Study Day 170.

Participants who do not have a Day 180 visit and have not already failed or been censored will be censored at (date of final parasite assessment) – (date of Study Day 1) days).

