Participant is parasite-free at 4 months. This is defined as a negative asexual *P. vivax* parasite count at the first parasite assessment performed on or after Study Day 105 (up to and including Study Day 135).

Participants who do not have a Day 120 visit and have not already failed or been censored will be censored at (date of final parasite assessment prior to Day 120) – (date of Study Day 1) days.

If a participant has a relapse outcome and a censored outcome, they will be considered to be a relapse, even if the time point of the relapse is later than the time point of censoring. For example, a participant who took a medication with anti-malarial activity at Study Day 32, but remained parasite-free after initial clearance until Study Day 68 will be treated as a relapse at Study Day 68.

Figure 2 Flowchart of algorithm for relapse-free efficacy at 4 months

Efficacy endpoints
Relapse free efficacy at 6 months missing=failure definition

In addition to those with a positive asexual P. vivax parasite count at any assessment prior to or on Study Day 190, the following participants will also be defined to have relapsed:
 
Participant did not demonstrate initial clearance of P. vivax parasitaemia (i.e. did not have two negative asexual P. vivax parasite counts, with at least 6 hours between the counts, and no positive counts in the interval)
 
Participant took a concomitant medication with anti-malarial activity at any point between Study Day 1 and their last parasite assessment. A list of all concomitant medications will be reviewed by a GSK clinician prior to unblinding the study, and classified accordingly.
 
Participant does not have a parasite assessment between Study Day 170 and 190.
 
Participants with a zero P. vivax asexual parasite count at baseline will be excluded from the analysis.

Genetic classification of relapse (heterologous/homologous)

Relapse-free efficacy at 6 months will be assessed separately according to whether the first P. vivax re-infection is homologous or heterologous to the original infection. The definition is as detailed above but heterologous infections will be censored at the time at which they occur for the endpoint looking at homologous infections only; and homologous infections will be censored at the time at which they occur for the endpoint looking at heterologous infections only.

Recrudescence

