11.11.2. Efficacy Tables

Efficacy: Tables					
No.	Population	IDSL / Example Shell	Title	Programming Notes	Deliverable
Parasite counts					
2.1	mITT	EFF_T1	Summary of P.vivax Asexual Parasites at all Timepoints		SAC
2.2	mITT	EFF_T1	Summary of Other Malarial Asexual Parasites at all Timepoints	Page by parasite	SAC
2.3	mITT	EFF_T1	Summary of P.vivax Gametocytes at all Timepoints		SAC
2.4	mITT	EFF_T1	Summary of Other Malarial Gametocytes at all Timepoints	Page by gametocyte	SAC
Relapse free efficacy					
2.5	mITT	EFF_T2	Summary of Relapse-Free Efficacy at 6 Months		SAC
2.6	mITT	EFF_T2	Summary of Relapse-Free Efficacy at 6 Months by Battalion		SAC
2.7	PP	EFF_T2	Summary of Relapse-Free Efficacy at 6 Months		SAC
2.8	mITT	TTE1	Survival Analysis of Relapse-free Efficacy over 6 months	See mock shells example template.	Headline
2.9	mITT	EFF_T7	Summary of Covariate and Treatment*Covariate Interaction Significance For Cox Proportional Hazards Model of Relapse-Free Efficacy Over 6 Months		SAC
2.10	PP	TTE1	Survival Analysis of Relapse-free Efficacy over 6 months		SAC
2.11	mITT	EFF_T3	Logistic Regression Analysis of Relapse-free Efficacy at 6 months (Subjects Censored Prior to 6 Months Excluded)	Add footnote: "Subjects who do not demonstrate initial clearance, take a concomitant medication with anti-malarial activity, have a missing Day 180 assessment, or have a zero P. vivax asexual parasite count at baseline are excluded from the analysis."	SAC

Efficacy: Tables					
No.	Population	IDSL / Example Shell	Title	Programming Notes	Deliverable
2.12	mITT	EFF_T3	Logistic Regression Analysis of Relapse-free Efficacy at 6 months (Missing = Failure Analysis)	Add footnotes: "Subjects who do not demonstrate initial clearance, take a concomitant medication with anti-malarial activity or have a missing Day 180 assessment are counted as relapses." "Subjects with a zero P. vivax asexual parasite count at baseline are excluded from the analysis."	SAC
2.13	mITT	TTE1	Survival Analysis of Genetically Heterologous Relapse-Free Efficacy over 6 Months – Homologous P. vivax Relapses Censored	Add footnote: Homologous relapses are censored at the point at which they occur.	SAC
2.14	mITT	TTE1	Survival Analysis of Genetically Homologous Relapse-Free Efficacy over 6 Months – Heterologous Relapses Censored	Add footnote: Heterologous relapses are censored at the point at which they occur.	SAC
2.15	mITT	EFF_T2	Summary of Relapse-Free Efficacy at 4 Months		SAC

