Number needed to treat per treatment group before one extra
success was seen compared to DHA-PQP only

Xx (xx,xx)

Xx (xx,xx)

[1] Subjects are censored if they did not have *P.vivax* at baseline, or took a drug with anti-malarial action despite not having malaria parasites, or did not have a 6 month assessment.

[2] Kaplan-Meier methodology

[3] Estimated from Cox's Proportional Hazards Analysis, adjusting for Battalion.

A hazard ratio < 1 indicates a lower chance of relapse compared to DHA-PQP only.

Population: Microbiologic Intent-to-Treat

EFF_T3
 Logistic Regression Analysis of Relapse-Free Efficacy at 6 Months (Subjects Censored Prior to 6 Months Excluded)

Treatment Group	N	n	Subjects Relapse Free (%)	Subjects Relapsed (%)	Comparison with DHA-PQP Only		
					Adjusted Odds Ratio of Relapse	95% CI	p-value
TQ+DHA-PQP	Xx	Xx	Xxx (xx%)	Xxx (xx%)	x.xx	(x.xx, x.xx)	0.xxx
PQ+DHA-PQP	Xx	Xx	Xxx (xx%)	Xxx (xx%)	x.xx	(x.xx, x.xx)	0.xxx
DHA-PQP Only	Xx	xx	Xxx (xx%)	Xxx (xx%)			

Note: Model includes terms for battalion and treatment.
 An odds ratio <1 represents a smaller chance of relapse compared to DHA-PQP only.

Population: Microbiologic Intent-to-Treat

TTE3

Analysis of Time to <Asexual Parasite Clearance>

	TQ+DHA-PQP (N=xxx)	PQ+DHA-PQP (N=xxx)	DHA-PQP only (N=xxx)
Number of Subjects			
Relapse	xx (xx%)	xx (xx%)	xx (xx%)
Censored	xx (xx%)	xx (xx%)	xx (xx%)
Estimates for Time to Clearance (Days) [1]			
1st Quartile	xx.x	xx.x	xx.x
95% CI	(xx.x, xx.x)	(xx.x, xx.x)	(xx.x, xx.x)
Median	xx.x	xx.x	xx.x
95% CI	(xx.x, xx.x)	(xx.x, xx.x)	(xx.x, xx.x)
3rd Quartile	xx.x	xx.x	xx.x
95% CI	(xx.x, xx.x)	(xx.x, xx.x)	(xx.x, xx.x)
Adjusted Hazard Ratio vs DHA-PQP only [2]			
Estimate	x.xx	x.xx	
95% CI	(x.xx, x.xx)	(x.xx, x.xx)	
p-value	x.xxx	x.xxx	
Adjusted Hazard ratio vs PQ+DHA-PQP [2]			
Estimate	x.xxx		
95% CI	(x.xxx, x.xxx)		

[1] Kaplan-Meier methodology

[2] Estimated from Cox's proportional Hazards Analysis, adjusting for Battalion.
 A hazard ratio <1 indicates a lower risk of [endpoint] compared to DHA-PQP only.

Population: Microbiologic Intent-to-Treat

EFF_T4

Incidence of Genetically Homologous and Genetically Heterologous *P. vivax* Infections (determined by PCR)

	TQ+DHA-PQP (N=xx)	PQ+DHA-PQP (N=xx)	DHA-PQP only (N=xx)
n [1]	Xx	Xx	Xx
P. vivax classified as genetically heterologous by PCR	Xx (xx%)	Xx (xx%)	Xx (xx%)
P. vivax classified as genetically homologous by PCR	Xx (xx%)	Xx (xx%)	Xx (xx%)

[1] n = number of subjects with an infection

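### The SAP censors participants who never clear P. vivax at 0 days where the protocol counts them as relapsed at 0 days, and SAP 2.1 does not declare the change

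*SAP*

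**What the plan says.** - **Endpoint.** Protocol 3 and SAP 2.2 both define the primary endpoint as "clearance of initial infection without subsequent microscopically confirmed recurrence during the 6 month follow up".
- **Protocol rule.** Protocol 9.4, in a bullet printed twice, says that a subject without initial clearance "will be considered to have relapsed with time to relapse = 0 days".
- **SAP rule.** SAP 11.6.3 defines clearance as two negative asexual counts at least 6 hours apart with no positive between them. Its sentence for the baseline-count criterion is "Participants who do not meet this criterion will be censored, with time to relapse censored at 0 days". The clearance criterion carries the same sentence, apart from one comma, in both the 6-month and the 4-month definitions.
- **Declared changes.** SAP 2.1 covers the GI endpoint, the populations, the blinded review, logistic regression in place of exact methods, and the model: "The primary analysis uses a Cox's proportional hazards model as opposed to the log rank test as described in the protocol". It says nothing about participants who do not clear.
- **Other SAP places.** The footnote to Table 2.11 excludes them ("Subjects who do not demonstrate initial clearance, take a concomitant medication with anti-malarial activity, have a missing Day 180 assessment"). The missing=failure definition counts them as relapses ("the following participants will also be defined to have relapsed"), together with users of anti-malarial drugs and those who "or have a missing Day 180 assessment are counted as relapses" (Table 2.12 footnote). Row 1 of shell EFF_T2 shows them by arm as not relapse-free. Footnote [1] of shell TTE1, used for the primary analysis table, gives the censoring reasons as no P. vivax at baseline, or "took a drug with anti-malarial action despite not having malaria parasites, or did not have a 6 month assessment". Failure to clear is missing from that list.

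**The concern.** The same participant is an event in one document and a non-event in the other, on the primary endpoint, and the section meant to list such changes is silent. Censoring at 0 days leaves a participant in the mITT count but gives him no weight in the partial likelihood or the Kaplan-Meier estimate. If parasites were seen to persist, a failure of the stated endpoint drops out of the hazard ratio.

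The SAP's rule that a relapse outcome overrides a censored one does not bring him back, because a relapse requires a positive count after initial clearance. The only planned model that counts him as a failure gives an odds ratio and merges him with two other kinds of case. The 4-month endpoint has no sensitivity analysis (SAP 7.2.5.1). What is at stake is the reported effect size and its traceability to the protocol.

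**Working it through.** **Who is affected.** Neither document sets a deadline for clearance in this endpoint, and smears run to Day 180. Two later negative smears, for example at Days 7 and 14, satisfy the SAP definition. A participant who is rescued, then clears and stays negative is censored under both documents through the anti-malarial criterion. The rules differ only for someone who never demonstrates clearance, because parasites persisted or because too few smears exist.

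**Inputs.** Protocol 9.2.1 gives 85% (TQ) and 50% (DHA-PQP alone) relapse-free at 6 months, 50 per arm, 10% withdrawal, and power above 90%. Protocol 9.1 gives a two-sided 5% test. The number of non-clearers is an assumption: 0 to 2 per arm. Protocol 4.4 cites over 95% blood-stage efficacy for DHA-PQP, which is fewer than 2.5 of 50, but that figure does not measure this open-ended criterion.

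**The plan's own figures.** Implied HR = ln 0.85 / ln 0.50 = 0.1625 / 0.6931 = 0.234. With 45 per arm after withdrawal, expected events are 45 × (0.50 + 0.15) = 29.25. The Schoenfeld formula gives 97.5% power and Freedman 91.8%, so the stated bound reproduces. Expected relapses are 25 + 7.5 + 7.5 = 40, and 40/150 = 26.7%, also as stated.

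**Protocol rule against SAP rule, 6 months.** With k non-clearers among 50, the protocol rule gives S = S(clearers) × (50 − k)/50. The SAP rule leaves S unchanged. The ratio is ln S(TQ) / ln S(control).

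| Non-clearers (TQ, control) | S(TQ) | S(control) | Difference, points | Ratio |
|---|---|---|---|---|
| SAP rule, any k | 0.850 | 0.500 | 35.0 | 0.234 |
| Protocol rule, 1 and 1 | 0.833 | 0.490 | 34.3 | 0.256 |
| Protocol rule, 2 and 2 | 0.816 | 0.480 | 33.6 | 0.277 |
| Protocol rule, 2 and 0 | 0.816 | 0.500 | 31.6 | 0.293 |
| Protocol rule, 0 and 2 | 0.850 | 0.480 | 37.0 | 0.221 |

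**Simulation.** Each scenario had 4,000 trials in each of two independent runs: exponential relapse detected at scheduled visits, 10% uniform withdrawal, two-arm Cox with Efron ties, 5% Wald test. The median HR under the SAP rule stayed at about 0.23. In the order of the four protocol rows, the protocol rule gave 0.256, 0.283–0.285, 0.303–0.307 and 0.213–0.216, with power 95.5–95.7%, 93.9–94.6%, 89.4–90.3% and 98.0–98.2%. In the newer run, SAP-rule power in these scenarios was 95.5–96.6%.

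**4 months.** Multiply both 6-month cumulative hazards by f and add −ln((50 − k)/50). With f assumed between 0.9 and 2/3 (constant hazard), the protocol rule gives 0.258–0.267, 0.281–0.297, 0.300–0.323 and 0.220–0.215, against 0.234 under the SAP rule.

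**If the cause is missing smears.** Suppose 2 per arm are non-clearers, of whom 1 is observed persistence (event) and 1 lacks smears (censored). Then S = 0.85 × 48/49 and 0.50 × 48/49, and the ratio is 0.1831 / 0.7138 = 0.257. If all merely lack smears and would relapse like the rest, 0.234 is the right value. The protocol rule then overstates it by 0.022 (1 per arm) or 0.043 (2 per arm).

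**The case against.** **Censoring has a basis in the text.** Both documents define relapse as recurrence after clearance, and the SAP's summary measure is the hazard of relapse. Someone who never clears has not relapsed in that sense, and blood-stage effect has its own endpoints. This stands as a reason the sponsor could give. It does not remove the conflict with Protocol 9.4 or with the endpoint wording, and SAP 2.1 does not give it.

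**A reader might infer that the SAP hides these participants.** It does not. EFF_T2 reports them by arm as not relapse-free in Tables 2.5 to 2.7 and, at 4 months, in Table 2.15. Listings EFF_L1 and EFF_L2 give each participant's reason for outcome and every dated smear, so persistence can be told from missing smears.

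**A reader might infer that the protocol rule is simply right for everyone.** The documents do not support that. Footnote 2 in SAP Appendix 1 records three participants whose positive smears were misread as negative and who then missed an assessment in Days 1–3. It does not say that they never cleared, but it shows how clearance data can be lost without treatment failure. An event at 0 days would then be an imputation. Balanced day-0 events also put a hazard ratio near 1 ahead of one near 0.23, which can strain the proportional-hazards check in SAP 7.1.5.1 and prompt its switch to logistic regression.

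**The numbers are speculative.** With no deadline, observed persistence without later clearance probably means leaving early while still positive. The assumed 1–2 cases per arm have no source.

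**Conclusion.** The conflict and the missing declaration are certain from the text. The size is not. With no non-clearers the two rules coincide. Under the planning rates with 1–2 observed persistent cases per arm, the 6-month ratio moves from 0.234 to 0.256–0.277. The computed extremes are 0.221 (2 in control only) and 0.293 (2 in TQ only).

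A reader might infer that the SAP rule is biased towards TQ. That holds for observed persistence that is balanced or confined to the TQ arm. It is slightly conservative if the cases are only in the control arm, and censoring may be the better estimate where smears are merely missing. The primary conclusion is unlikely to change, since simulated power stays at about 89% or more in every scenario shown. The change should be reconciled because it alters the event rule of the primary endpoint and no planned analysis shows its effect separately.

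**What to change.** 1. Reconcile the documents. Either restore the Protocol 9.4 rule in SAP 11.6.3 for both time points, or keep censoring and declare and justify it in SAP 2.1.
2. Whichever rule is primary, run the other as a Cox/Kaplan-Meier sensitivity analysis at 6 and 4 months.
3. Where clearance cannot be judged only because smears are missing or misread, censoring may be kept with that reason stated.
4. Align footnote [1] of shell TTE1 with the rule chosen.

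Optional: split EFF_T2 row 1 into observed persistence and missing smears, and state by when clearance must be shown for this endpoint.

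**Cost.** SAP wording, one derivation, and one added sensitivity analysis at each of the two time points. If the protocol rule is used, the hazard ratio may be less favourable, with simulated power of about 89–90% for 2 cases in the TQ arm only. Anyone who only lacks smears is counted as a failure unless step 3 is adopted, and day-0 events may affect the proportional-hazards check.

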If a participant has a relapse outcome and a censored outcome, they will be considered to be a relapse, even if the time point of the relapse is later than the time point of censoring. For example, a participant who took a medication with anti-malarial activity at Study Day 32, but remained parasite-free after initial clearance until Study Day 68 will be treated as a relapse at Study Day 68.

Figure 1 Flowchart of algorithm for relapse-free efficacy at 6 months

Relapse free efficacy at four months

Relapse is defined as any recurrence of *P. vivax* malaria after clearance of the initial infection.

Participants will be considered to have demonstrated relapse-free efficacy at four months if all of the following are true (also described in [Figure 2](#)):

Participant had a non-zero *P. vivax* asexual parasite count at baseline. Participants who do not meet this criterion will be censored, with time to relapse censored at 0 days.

Participant demonstrated initial clearance of *P. vivax* parasitemia. This is defined as two negative asexual *P. vivax* parasite counts, with at least 6 hours between the counts, and no positive counts in the interval. Participants who do not meet this criterion will be censored with time to relapse censored at 0 days.

Participant has no positive asexual *P. vivax* parasite count at any assessment prior to or on

Efficacy endpoints

Study Day 135 following initial parasite clearance. Participants who do have a positive count will be considered to have relapsed with time to relapse = (date of first positive count) – (date of Study Day 1) days.

[figure not shown]
Participants did not take a concomitant medication with anti-malarial activity (excluding study treatment) at any point between Study Day 1 and their first parasite assessment after Study Day 105 (up to and including Study Day 135). Participants who did take a drug with anti-malarial activity but never had a positive asexual *P. vivax* parasite count after initial clearance will be censored with time to relapse censored at (date of last negative parasite assessment prior to concomitant medication start) – (date of Study Day 1) days. If a participant has not had a negative assessment prior to the concomitant medication start date, they will be censored at 0 days.

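### The crude 4-month table (Table 2.15) counts a man who missed Day 120 as not relapse-free even when he is a 6-month success, and its lower bound of Day 105 belongs to the Day 90 visit

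*SAP*

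**What the plan says.** SAP 11.6.3 defines the 4-month endpoint by a list of conditions that must all hold: "Participants will be considered to have demonstrated relapse-free efficacy at four months if all of the following are true". They cover a positive baseline count, initial clearance, no positive count up to Study Day 135, no anti-malarial drug, and a confirming smear. Three sentences matter here.

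- Confirming smear: a zero result is required for the "parasite count at the first parasite assessment performed on or after Study Day 105 (up to and including Study Day 135").
- Anti-malarial criterion: use is assessed up to "their first parasite assessment after Study Day 105 (up to and including Study Day 135").
- Missed visit: "Participants who do not have a Day 120 visit and have not already failed or been censored will be censored at" the time given by ("date of final parasite assessment prior to Day 120) – (date of Study Day 1) days").

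The 6-month definition in the same section has parallel conditions, but its confirming smear is a negative "parasite count at the first parasite assessment performed on or after Study Day 170". It does not ask for a smear at Day 120.

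SAP 11.3.1 (Appendix 3) assigns Days 76 to 105 to the Day 90 visit and Days 106 to 135 to the Day 120 visit.

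Two outputs serve the 4-month objective. Table 2.15 gives n (%) per arm on shell EFF_T2. Table 2.16 gives Kaplan-Meier rates and hazard ratios. SAP 7.2.5.1 plans no sensitivity analysis for this endpoint.

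**The concern.** Being relapse-free through six months entails being relapse-free through four. The two definitions should therefore be nested, and they are not: the 4-month rule ignores negative smears taken after Day 135, although the data are in hand.

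Shell EFF_T2 is drafted for six months and is reused for Table 2.15. Men without the endpoint assessment who meet no other criterion go into its row for those not confirmed parasite-free, and its note says that anyone in such a row is not relapse-free. So the crude table that reports on a named secondary objective can contradict the same man's entry in Table 2.5.

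The Day 105 wording is a second, smaller problem. Two bullets of one definition use different first days, and one of them does not match the visit window, so two programmers could classify the same man differently.

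**Working it through.** **Windows.** The offsets in the Protocol 7.1 Time and Events Table reproduce the limits in SAP Appendix 3:

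- Day 90: 90 − 14 = 76 to 90 + 15 = 105
- Day 120: 120 − 14 = 106 to 120 + 15 = 135
- Day 180: 180 − 10 = 170 to 180 + 10 = 190

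The 6-month lower bound (170) and the 4-month upper bound (135) match their windows. The 4-month lower bound does not: 105 is stated, 106 follows from the window. The anti-malarial bullet, which starts after Day 105, agrees with 106.

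**Tracing the rules.** All smears are negative, the initial infection is cleared and no anti-malarial is taken.

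| Smears on Study Days | 6 months | 4 months |
|---|---|---|
| 28, 60, 90, 120, 150, 180 | success | success |
| 28, 60, 90, 150, 180 | success | no confirming smear; censored at 90 − 1 = 89 days |
| 28, 60, 150, 180 | success | no confirming smear; censored at 60 − 1 = 59 days |
| 28, 60, 105, 150, 180 | success | meets the confirming-smear bullet, yet has no Day 120 visit, so censored at 105 − 1 = 104 days |

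Rows 2 and 3 show the lack of nesting. Row 4 shows the Day 105 contradiction: the man meets both the success rule and the missed-visit rule.

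**Size in Table 2.15.** Inputs: the 6-month relapse-free rates of 50% (DHA-PQP alone) and 85% (with tafenoquine; primaquine is the same) from Protocol 9.2.1. Assumptions: constant hazard, no withdrawals, and a fraction m of event-free men missing Day 120, taken as 2%, 5% and 10%.

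S(t) = s₆^(t/180), so S(135) = 0.50^0.75 = 0.595 and 0.85^0.75 = 0.885. The crude rate is S(135) × (1 − m), and the understatement is S(135) × m.

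| m | DHA-PQP alone: 59.5% becomes | loss, points | Tafenoquine: 88.5% becomes | loss, points |
|---|---|---|---|---|
| 2% | 58.3% | 1.2 | 86.8% | 1.8 |
| 5% | 56.5% | 3.0 | 84.1% | 4.4 |
| 10% | 53.5% | 5.9 | 79.7% | 8.9 |

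Using S(120) = 0.630 and 0.897 instead gives losses of 1.3, 3.2 and 6.3 points, and 1.8, 4.5 and 9.0 points.

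Men who are outright 6-month successes but 4-month non-successes number 50 × m × s₆ per arm: 0.5, 1.3 and 2.5 on DHA-PQP alone, and 0.9, 2.1 and 4.3 on tafenoquine.

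**Size in Table 2.16.** These men are censored, not counted as relapses. If visits are missed at random the Kaplan-Meier rate has no expected bias. The worst case is that every relapse between Days 90 and 135 is still detected by Day 135 while the event-free men who miss the visit leave at Day 90. Then

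KM = S(90) × [1 − (S(90) − S(135)) / (S(90) − m × S(135))].

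At m = 10%:

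- DHA-PQP alone: 0.7071 × [1 − 0.1125/0.6476] = 0.584 against 0.595, about 1.0 point low.
- Tafenoquine: 0.9220 × [1 − 0.0367/0.8334] = 0.881 against 0.885, about 0.4 points low.

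**The case against.** The best defence is that the planned inference for four months is the survival analysis, where censoring at the last smear is conventional and mirrors the 6-month rule for a missing endpoint visit. Table 2.15 shows unconfirmed men in their own row, apart from recurrences. Missed visits may also be few: the Day 120 window is 30 days long, the clinic is on the army base and always open, and an unscheduled smear on Days 106 to 135 is slotted to Day 120. The missed-visit rates above have no source in the documents. The Day 105 question matters only for a man whose sole smear in the window falls on that day.

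Most of this stands, and it limits the point to Table 2.15 and one day of wording. The analogy with six months fails for the crude count, however. At six months no later smear may be used, because Protocol 9.4 makes the Day 180 visit the last source of data. At four months the Day 150 and Day 180 smears exist and settle the question.

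A reader might infer three stronger things that the documents do not support.

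- *The treatment contrast shrinks.* Shell EFF_T2 gives counts and percentages per arm, with no between-arm difference, interval or p-value.
- *Table 2.16 understates efficacy.* That needs the one-sided detection pattern in the worst case above, and even then is about 1 point or less at 10% missing.
- *Every man lost is a non-relapser.* A man negative at Day 90, absent at Day 120 and first positive at Day 150 is censored in the same way.

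**Conclusion.** The point holds for Table 2.15 and for the Day 105 boundary. By its text, the plan reports a man as not relapse-free at four months when its own 6-month rule shows that he was. The crude 4-month rate is low by S(135) times the fraction missing Day 120: about 1.2 to 5.9 points on DHA-PQP alone and 1.8 to 8.9 points with tafenoquine for 2% to 10% missing. Those sizes rest on constant hazards at the design rates and on assumed missed-visit rates; the contradiction itself rests on neither.

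The Day 105 mismatch is a real internal contradiction of one day and will touch very few men. The 4-month flowchart (Figure 2) is not visible in the text available, so it cannot be said to resolve or repeat it.

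The primary endpoint is unaffected and the Table 2.16 censoring rule can stand. This is a minor, inexpensive correction.

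**What to change.** 1. In Table 2.15, count as relapse-free at four months any man who meets the 6-month relapse-free definition, or who has a negative smear after the window with no intervening positive smear or anti-malarial use. This cannot credit a man who has a recorded recurrence by Day 135. It does not recover every lost man: those whose next smear is positive stay unconfirmed. If the next smear is on Day 150, the gain is m × S(150), with S(150) = 0.561 and 0.873; at m = 10% that is 5.6 of the 5.9 points lost on DHA-PQP alone and 8.7 of 8.9 on tafenoquine.
2. In the confirming-smear bullet, start the window on Study Day 106, so that both bullets and Appendix 3 agree and no Day 90 smear can certify the 4-month result. Check Figure 2 for the same limit.

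Leave the Table 2.16 censoring as it is. It is tempting to carry men to Day 135 there whenever a later smear is negative, but that keeps future negatives at risk while future positives leave at Day 90. With 10% missing and detection only at visits, on DHA-PQP alone the number at risk is 0.7071 × [1 − 0.10 × (1 − 0.794)] = 0.6925 and the events are 0.90 × (0.7071 − 0.6300) = 0.0694. The Day 120 rate becomes 0.7071 × (1 − 0.0694/0.6925) = 63.6% against a true 63.0%, an upward bias of about 0.6 points.

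The cost is two sentences in SAP 11.6.3 and a programming note for Table 2.15, with no new data. Make the change before unblinding, or otherwise report it as a clarification in the study report.
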